Patients under 10 kg in body weight will have the CPB pump primed with one unit of Packed Red Blood Cells (PRBC) and 200 cc Fresh Frozen Plasma (FFP). In patients over 10 kg a pure crystalloid prime will be used. Target hemoglobin (Hg) while on CPB will be 9 gm/dL, but the transfusion trigger for additional units of PRBC will be 7 gm/dL.

Drug protocol:

The following laboratory studies will be obtained prior to surgery: Complete Blood Count (CBC), Prothrombin time (PT), International Normalized Ratio (INR), Partial Thromboplastin time (PTT), Platelet count, and a Fibrinogen level; an electrolyte profile will also be done. An Activated Clotting Time (ACT) and a Thromboelastometry analysis [REDACTED], a device that assesses the viscoelasticity of whole blood and other parameters, will be done after an A-line is placed (Figure 1).

A blood products transfusion algorithm was developed based on four previous studies published in the literature, modified for pediatrics¹⁶¹⁷¹⁸¹⁹ (Figure 2). Blood is measured in the cell saver reservoir and the suction canister every fifteen minutes while in the OR. Clinically significant bleeding, requiring treatment, will be defined as a rate in excess of 10 cc/kg/hr calculated every 15 minutes while in the OR. Calculations will be done every 60 minutes in the CICU.

After rewarming, but prior to the termination of CPB a ROTEM analysis will be done. Platelets or FFP will be administered at this time, while still on CPB, if the ROTEM results indicate a deficiency of either component. Then immediately after the termination of CPB, RiaSTAP or NS will be administered depending on the group assignment. Then, as per routine care, a ROTEM analysis and fibrinogen level will be assessed and the transfusion algorithm will be continued. *If the ROTEM indicates a fibrinogen deficiency, cryoprecipitate will be given.* Thereafter, as per routine care, a ROTEM analysis will be done at least every 30 minutes while in the OR or sooner at the discretion of the OR team. Once the patient leaves the OR a ROTEM will be done at least every 60 minutes for the first six hours or until clinically significant bleeding has stopped, whichever comes first; ROTEMs can be done more frequently at the discretion of the ICU staff caring for the patient. The blood products transfused after separation from CPB will be based on the protocol below (Figure 3). Dosing amounts of the required component therapy will be based on the formula below:

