PRBC: Volume required = Blood volume (V) x desired Hct increase / Hct of red cell unit (70%)

FFP: 20 cc/kg

Plateletpheresis: 20 cc/kg

Cryoprecipitate: 10 cc/kg

The ROTEM analysis algorithm is below (Figure 4).

Four main scenarios based on clinical observation and TEM results were possible:

1. Insignificant bleeding—normal TEM \Rightarrow no transfusions
2. Insignificant bleeding—abnormal TEM \Rightarrow no transfusions
3. Significant bleeding—normal TEM \Rightarrow surgical reevaluation
4. Significant bleeding—abnormal TEM \Rightarrow transfusion of blood products as indicated by:
 - a. fib-TEM MCF < 7 mm \Rightarrow cryoprecipitate
 - b. hep-TEM MCF < 50 mm \Rightarrow platelets,
 - c. hep-TEM CT > 240 seconds \Rightarrow FFP,
 - d. hep-TEM CFT > 110 seconds \Rightarrow cryoprecipitate and /or platelets depending on MCF

If clinically indicated (continuing bleeding) or to verify the treatment effect and control heparin reversal, a second set of in-TEM, hep-TEM, and fib-TEM analyses will also be performed during wound closure. ACT will be tested in all patients to control for heparin reversal. If patients have both a pathological ACT and TEM, protamine will be administered.

Postoperative bleeding in the ICU will be defined as the total amount of chest tube drainage after closure of the sternum and during the first 24 postoperative hours. If the sternum is not closed, it will be defined as the total chest tube drainage during the first 24 postoperative hours. An intensive care nurse blinded to group assignment will record the bleeding every hour. The amount of transfused red blood cells (RBC), FFP, cryoprecipitate and platelets during the hospital stay will be recorded in cc/kg. The transfusion triggers will be as described above. The CICU physicians and nurses will not be informed of the preoperative fibrinogen concentration or group assignment.

Patient Assessment:

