3. Time in/out, sternal closure time, bypass start/stop time, total bypass time, total cross clamp time, total regional low perfusion time, blood components administered for patients under 10 kg in body weight, and pure crystalloid prime for patients over 10 kg in body weight, activated clotting time (ACT), thromboelastometry analysis after A-line assessment.
4. During intraoperative period concomitant medications include anesthesia induction medication, heparin, and protamine.
5. Estimated blood loss will be assessed every 15 minutes while in the OR and every 60 minutes in the CICU. Clinically significant bleeding defined as a rate in excess of 10 cc/kg/hr.
6. Total EBL at 24 hour time point.
7. Prior to Termination of CPB
8. If bleeding occurs
9. If fibrinogen deficiency noted on ROTEM, administer cryoprecipitate
10. Every 30 minutes as routine or sooner as per OR team discretion.
11. Assess post-operatively for every hour for 6 hours or until clinically significant bleeding ceases and additionally as per ICU team's discretion.
12. Includes total prime, total CPB, total Anesthesia, total CICU, total platelets, total PRBC, total FFP, total Cryo, total cell saver.
13. Assess every 8 hours central and arterial line for signs and symptoms. Thrombosis including edema, leg pain and tenderness, erythema, and discoloration for venous thrombosis, loss of distal peripheral pulses, pain, pallor, paresis, paresthesias, decreased skin temperature for arterial thrombosis. Confirmed by Doppler Ultrasound. Report when occurs.
14. Any untoward event reported from the time subject signs consent. Should be reported as soon as the study team becomes aware.

Data Analysis and Data Monitoring

Safety Monitoring

For the safety monitoring, adverse events will be documented. Aggregate and individual subject data related to safety, data integrity and overall conduct of the trial will be reviewed after enrollment of 10, 20 and 30 subjects.

Methods to Minimize Bias

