To avoid selection bias, patients will be randomized to their treatment assignment group by the research pharmacists using the Research Randomizer. The randomization procedures are detailed in the Methods and Procedures section of this protocol. All operating room and ICU personnel will be blinded to the patient's Group assignment. An intensive care nurse blinded to group assignment will record postoperative bleeding every hour. Since the study is blinded and the practitioners caring for the patient will not know if the subject received the study drug or placebo, for the study treatment period (ending 24 hours after surgery), the Cardiac Intensive Care Unit staff will monitor the incidence of adverse thromboembolic events and intervene with routine care, if necessary. In order to maintain patient safety, the ROTEM analyses must be interpreted by the anesthesiologist caring for the patient in order to guide transfusion therapy. This is the standard of care and an integral part of the protocol. The hospital staff anesthesiologists are also investigators in the study including the Principal Investigator. As part of routine care, if the ROTEM results indicate a deficiency of platelets or FFP, either component will be administered while still in the OR. In addition, if the ROTEM indicates a fibrinogen deficiency after termination of CPB, cryoprecipitate will be given. After review of the ROTEM values, the identity of the study drug may be discernable. In order to avoid the ascertainment bias from this knowledge, study data will be analyzed by a biostatistician independent of the investigator prior to any presentation or publication of study results. The biostatistician will be blinded to the study treatment assignment.

Statistical Analyses

All quantitative measures will be analyzed using descriptive statistics [mean +/- standard deviation (SD), etc.]. Treatment and placebo group comparisons will be made with the Student's t-test (continuous variables) or Fisher's exact test (categorical variables). A p-value of ≤ 0.05 will be considered statistically significant. For group comparisons of variables that will be analyzed at more than onetime point, Analysis of Variance (ANOVA) for repeated measurements will be used followed by Student's t-test if the ANOVA (group or interaction between group and time) indicated a statistically significant difference ($p \leq 0.05$).

Data Storage and Confidentiality

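### The protocol gives two conflicting triggers for cryoprecipitate, one with and one without a bleeding condition, and cryoprecipitate volume is part of a primary efficacy endpoint

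*Combined protocol and SAP*

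**What the plan says.** Three statements tie cryoprecipitate to the ROTEM result alone:

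- Methods and Procedures, Drug protocol, on the ROTEM taken after RiaSTAP or saline: "If the ROTEM indicates a fibrinogen deficiency, cryoprecipitate will be given".
- Schedule of Events, footnote 9, attached to the ROTEM row: "If fibrinogen deficiency noted on ROTEM, administer cryoprecipitate".
- Methods to Minimize Bias: "if the ROTEM indicates a fibrinogen deficiency after termination of CPB, cryoprecipitate will be given".

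The four-scenario list in the Drug protocol section adds a bleeding condition. Scenario 2, "Insignificant bleeding—abnormal TEM", leads to no transfusion. Cryoprecipitate appears only in scenario 4, "Significant bleeding—abnormal TEM", either through item 4a ("fib-TEM MCF < 7 mm") or through item 4d, which rests on clot formation time. The threshold for bleeding comes from the same section: "Clinically significant bleeding, requiring treatment, will be defined as a rate in excess of 10 cc/kg/hr calculated every 15 minutes while in the OR". In the CICU the rate is calculated hourly.

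The cryoprecipitate dose is fixed at 10 cc/kg. Under Endpoints and again under Patient Assessment, the volume transfused in cc/kg is a primary efficacy endpoint, and Endpoints asks for it by component.

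**The concern.** The two sets of statements disagree about one kind of patient: the infant whose ROTEM shows low fibrinogen but who is not bleeding significantly. The team needs one instruction for that infant, and the protocol supplies two.

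The analysis is affected because the trigger and the intervention are linked. The study drug is fibrinogen, and Figure 1 describes the fib-tem assay as a measure of fibrinogen level and quality, so the drug is expected to raise FIBTEM. A placebo infant may therefore receive cryoprecipitate because FIBTEM was not raised, even if bleeding is the same in both arms. How much of the arm difference arises this way depends on which rule is followed.

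Mixed use of the rules adds variance. It could also add bias: Methods to Minimize Bias concedes that the ROTEM values may reveal the study drug to the anesthesiologists, who interpret them to guide transfusion and are also investigators. Two available rules leave such a clinician discretion over part of a primary endpoint, and a blinded biostatistician cannot undo that afterwards.

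**Working it through.** The plan states no figure for cryoprecipitate use, so there is none to reproduce. The check compares the text and then sizes the effect under stated assumptions.

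**1. The rules side by side**, taking deficiency as FIBTEM below the 7 mm cut-off of item 4a:

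| Bleeding | ROTEM | Deficiency-only statements | Four-scenario list |
|---|---|---|---|
| Not significant | Normal | None | None |
| Not significant | Low FIBTEM | Cryoprecipitate, 10 cc/kg | None |
| Significant | Normal | None | Surgical re-evaluation |
| Significant | Low FIBTEM | Cryoprecipitate, 10 cc/kg | Cryoprecipitate, 10 cc/kg |

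For cryoprecipitate the rules conflict only in the second row.

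**2. Size per discordant infant.** Inputs from the documents: 10 cc/kg per dose and 15 infants planned per group. Assumption: one dose per infant. If k more placebo than treated infants fall in the second row, the difference in mean volume between the two rules is

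shift = 10 × k / 15 cc/kg.

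- k = 1: 10/15 = 0.7 cc/kg
- k = 3: 30/15 = 2.0 cc/kg
- k = 6: 60/15 = 4.0 cc/kg

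The values of k are assumed.

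**3. Laboratory-driven difference under each rule.** Let pC and pT be the proportions with low FIBTEM after study drug on placebo and on RiaSTAP. Let s be the proportion bleeding significantly, equal in both arms and independent of FIBTEM. Item 4d is ignored. Then

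- deficiency alone: difference = 10 × (pC − pT)
- deficiency plus significant bleeding: difference = 10 × s × (pC − pT)

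| Assumed pC v pT | Deficiency alone | With bleeding, s = 0.2 | s = 0.4 | s = 0.6 |
|---|---|---|---|---|
| 40% v 10% | 3.0 | 0.6 | 1.2 | 1.8 |
| 60% v 10% | 5.0 | 1.0 | 2.0 | 3.0 |
| 80% v 20% | 6.0 | 1.2 | 2.4 | 3.6 |

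(All in cc/kg.) Bleeding is identical in the two arms throughout, yet neither rule gives zero. Moving from the first rule to the second removes a fraction 1 − s of the difference, which is 40% to 80% here.

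Steps 2 and 3 agree. The expected k is 15 × (1 − s) × (pC − pT). For 60% v 10% and s = 0.2 this is 15 × 0.8 × 0.5 = 6, a shift of 4.0 = 5.0 − 1.0 cc/kg.

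**4. Effect on the test.** For the number of infants given cryoprecipitate, 15 per arm and 60% v 10%, Fisher's exact test reaches p ≤ 0.05 in 74% of trials under deficiency alone. Under the bleeding condition it does so in 2%, 17% and 38% of trials for s = 0.2, 0.4 and 0.6. With 15 per arm and two-sided 0.05, 80% power needs a difference of about (1.96 + 0.84) × √(2/15) = 1.02 SD, so added variance from mixed rules is costly.

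**The case against.** The strongest defence is that the short statements abbreviate scenario 4. In the Drug protocol section the sentence just before the cryoprecipitate line says that "a ROTEM analysis and fibrinogen level will be assessed and the transfusion algorithm will be continued". The same paragraph refers products given after bypass to Figure 3, and the text on ICU bleeding refers back to the triggers already described. None of the three short statements gives a numerical threshold; the FIBTEM cut-off appears only in item 4a. Footnote 9 is attached to the whole ROTEM row, including the pre-operative column, so it is hard to read as a complete rule. Methods to Minimize Bias is not an order set.

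This makes the shorthand reading plausible, most of all for the Drug protocol line. It does not settle the matter, because no sentence makes the short statements subject to the bleeding condition. The protocol also uses laboratory-only triggering elsewhere: platelets or FFP are given on bypass if the ROTEM indicates a deficiency. The graphics of Figures 2 to 4 are not available here. They may show the intent, but they would not remove the conflict in the written text.

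Two further points stand. The size is illustrative, because the documents give no rate of low FIBTEM without significant bleeding. And the Purpose of Study includes reducing the need for component therapy, so less cryoprecipitate because fibrinogen has already been replaced may be an intended effect. That is a reason to report the two sources of the difference separately, not to leave the trigger unclear.

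A reader might infer that a bleeding condition would free the endpoint of the laboratory effect. Item 4a does not support this: among significant bleeders, FIBTEM still decides who receives cryoprecipitate.

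**Conclusion.** The contradiction is in the current text and should be corrected. It is confined to infants with low FIBTEM and no significant bleeding, each of whom accounts for 10 cc/kg under one rule and 0 under the other. Both rules let the laboratory value drive part of the arm difference in cryoprecipitate; the deficiency-only rule does so to a larger degree. The shift is 10k/15 cc/kg, for example 0.7 to 4.0 for k = 1 to 6. This assumes one dose per infant and 15 per arm, with k not known from the documents.

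A reader might also infer that teams did apply different rules, or that the cryoprecipitate result is biased. The documents do not show either. They show that the text permits it, and that the clinicians ordering the product may be able to discern the assignment. Which trigger is clinically right is not judged here.

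**What to change.** - **Wording.** Reconcile the Drug protocol statement, the four-scenario list, footnote 9 of the Schedule of Events and Methods to Minimize Bias into one cryoprecipitate trigger, applied identically in both arms. The clinical team decides which. Check that Figures 2 to 4 agree with it.
- **Data.** For each cryoprecipitate order, record the current bleeding rate and the most recent FIBTEM MCF with its time. The time is needed because a concurrent value is not assured for later ICU orders: hourly ROTEM runs only for six hours or until significant bleeding stops, and Table 1 otherwise schedules ROTEM at hours 2 and 24 or as needed.
- **Reporting.** Give cryoprecipitate volume by arm, split by whether significant bleeding was present at the order.

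Cost: protocol wording and two or three CRF items per cryoprecipitate order. No extra tests are needed.

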Both Groups will receive the normal standard of care both before and especially after this event. This will be the only event that is different for the two groups. To avoid selection bias, the Pharmacy will perform the randomization using Research Randomizer. Briefly, for each patient, a randomly generated integer between 1-30 will be produced. If the number is even, the patient will be assigned to Group 1. If the number is odd, the patient will be assigned to Group 2. The randomization process and schedule will be provided by the Principal Investigator's office, but the actual patient assignment will be done by Pharmacy.

All operating room and ICU personnel will be blinded to the patient's Group assignment. The only persons who will have access to the identity of the Group assignment from the time of randomization until 24 hours after surgery will be members of the Pharmacy staff. NONE of these individuals will be involved in patient care. The DSMB will be unblinded AFTER the study treatment period concludes (24 hours after surgery).

Endpoints:

Primary efficacy endpoints will be estimated as follows:

- postoperative bleeding (EBL) during the first 24 hours (hr) after surgery (cc/kg),
- the identity and total volume of transfused blood products (cc/kg) given in the peri-operative period, separated out into its components,
- hemoglobin concentration 2 hr. and 24 hr. after surgery and
- effects of fibrinogen infusion on global hemostasis 2 hr. and 24 hr. after surgery (PT, PTT, INR, fibrinogen level, platelet count and ROTEM analysis).

Post-operative period begins after the patient leaves the operating room. The need for Factor VII use and dose will also be included as a primary end point. Factor VII is typically used only if there is profuse bleeding not amenable to component transfusion therapy.

Secondary end points will include:

- the number of post-op hours requiring ventilator support,
- Length of Stay (LOSH) in the hospital,
- Length of Stay (LOS ICU) in the Cardiac Intensive Care Unit (CICU) and
- the need for re-exploration for bleeding within the first 12 hours.

The primary safety endpoints that will be monitored are the presence of a clinical adverse events. Clinical adverse events (AEs) are defined as any clinical signs of central or peripheral thromboembolism, respiratory or circulatory failure, or allergic reactions during hospital stay. It will also include infection with a blood-borne pathogen.

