Primary efficacy endpoints will be postoperative bleeding during the first 24 hours (hr) after surgery (cc/kg), the total volume and identity of transfused blood products (cc/kg), hemoglobin concentration 2 hr. and 24 hr. after surgery and effects of fibrinogen infusion on global hemostasis 2 hr. and 24 hr. after surgery (PT, PTT, INR, fibrinogen level, platelet count and ROTEM analysis). Secondary end points will include the number of post-op hours requiring ventilator support, Length of Stay (LOS) in the Cardiac Intensive Care Unit (CICU), the need for re-exploration for bleeding within the first 12 hours, and LOS in the hospital. The need for Factor VII use and dose will also be included.

The primary safety endpoint is a clinical adverse event. Clinical adverse events are defined as:

1. Any clinical signs of central or peripheral thromboembolism. This will then be confirmed by Doppler ultrasound. Assessments will be made once per shift (once every eight hours)
2. Respiratory or circulatory failure. Parameters of respiration, like respiratory rate (RR), end-tidal CO₂ (ETCO₂) and circulation, like heart rate (HR), rhythm, blood pressure (BP), arterial oxygen saturation (SpO₂) are monitored continuously while in the ICU. Respiratory failure will be defined as the need for reintubation after extubation. Circulatory failure will be defined as cardiac arrest.
3. Allergic reactions during hospital stay. These will include signs or symptoms like urticaria, wheezing, angioneurotic edema, and anaphylaxis.
4. Infection with a blood borne pathogen. Manifestation of an infection with a blood borne pathogen is unlikely to occur during the study treatment period, which ends 24 hours after the end of surgery. If this were to occur, it would not manifest itself for weeks or even months.

Patients will be assessed once per shift (once every eight hours) for signs of thromboembolism. Any evidence of thromboembolism will warrant a vascular ultrasound to assess the integrity of the vessel.

Adverse events will be monitored until discharge.

All patients will be assessed for signs and symptoms of thromboembolism, per routine care. Specifically, patients will be assessed for signs and symptoms of central and arterial

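### Read literally, the 24-hour bleeding endpoint drops drainage before sternal closure for an infant whose chest is left open at OR exit and closed in the CICU within 24 hours

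*Combined protocol and SAP*

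**What the plan says.** - **Endpoints.** Bleeding over 24 hours, in cc/kg, is listed first among the primary efficacy endpoints and is labelled EBL. The clock is given separately: "Post-operative period begins after the patient leaves the operating room".
- **Drug protocol, paragraph on bleeding in the ICU.** Postoperative bleeding is "the total amount of chest tube drainage after closure of the sternum and during the first 24 postoperative hours". A second rule follows: "If the sternum is not closed, it will be defined as the total chest tube drainage during the first 24 postoperative hours". A blinded nurse records the drainage hourly.
- **Patient Assessment.** The endpoint is repeated as bleeding after surgery, with no start event named.
- **Schedule of Events, footnotes 5 and 6.** "Estimated blood loss will be assessed every 15 minutes while in the OR and every 60 minutes in the CICU", and then "Total EBL at 24 hour time point". Footnote 6 names no start.
- **Drug protocol, on OR measurement and study drug.** OR loss is read from the cell saver reservoir and suction canister. Study drug or saline is given as soon as bypass ends, so sternal closure comes after treatment.
- **Schedule of Events, footnote 3.** Sternal closure time is recorded with the surgical and bypass data, a row marked only in the intraoperative column.
- **Statistical Analyses.** Continuous variables are compared by Student's t-test. Nothing there says which bleeding window is analysed.

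**The concern.** The window for a primary endpoint should be fixed by something treatment cannot move. Here one limit of the window is sternal closure, which happens after study drug. Two infants with the same hourly drainage can therefore get different values because one chest was closed in the CICU and the other was not.

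If such closures are equally common and similarly timed in the two arms, the main cost is added variability in a trial of 15 per arm. If their frequency or timing differs by arm, the comparison of means is biased: the arm with more CICU closures appears to bleed less.

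The quantity measured is also unsettled. The Endpoints section calls it EBL, which is collected in the OR as well as the CICU, while the ICU definition counts chest tube drainage only.

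**Working it through.** **No figure to reproduce.** The plan gives no expected drainage, SD, effect size or frequency of delayed closure. The check is a comparison of the texts, followed by illustrations under stated assumptions.

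**Step 1: the texts side by side.** Take the ICU definition with the OR-exit clock from the Endpoints section. Its conditions apply jointly: in the ICU, after sternal closure, and within the first 24 postoperative hours.

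| Sternal course | Window that results |
|---|---|
| Closed in the OR | OR exit to 24 h |
| Never closed within 24 h | OR exit to 24 h (second rule) |
| Open at OR exit, closed in the CICU at hour c < 24 | Hour c to 24 h, if the first rule applies literally |

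The first two rows agree with each other and with the Endpoints section. Only the third departs, and no section addresses it.

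**Step 2: drainage lost for one infant in the third row.** Let the rate be constant, or proportional to exp(−t/τ) from OR exit (both assumed). The fraction kept after closure at hour c is

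- constant rate: (24 − c)/24
- decaying rate: (e^(−c/τ) − e^(−24/τ)) / (1 − e^(−24/τ))

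| Closure at (assumed) | Constant | τ = 12 h | τ = 6 h | τ = 4 h |
|---|---|---|---|---|
| 6 h | 75% | 54.5% | 35.6% | 22.1% |
| 12 h | 50% | 26.9% | 11.9% | 4.7% |
| 18 h | 25% | 10.2% | 3.2% | 0.9% |

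For example, at c = 12 and τ = 6: (0.1353 − 0.0183)/(1 − 0.0183) = 0.119.

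**Step 3: when this becomes bias.** Assume no treatment effect, mean 24-hour drainage of 20 cc/kg, and CICU closure times uniform on 6 to 20 h (mean 13 h). At a constant rate an affected infant loses on average 13/24 = 54.2% of the total. If CICU closure occurs in 10% of one arm and 30% of the other, the false difference in means is (0.30 − 0.10) × 0.542 × 20 = 2.2 cc/kg. At 10% vs 50% it is 4.3 cc/kg. If both arms have 10%, it is zero.

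A simulation on the same assumptions used 15 per arm, lognormal drainage with CV 0.5 or 0.8, constant rate or τ = 6 h, a two-sided t-test at 0.05 and 20,000 runs per setting. It gave these null rejection rates:

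| CICU closure, arm A vs arm B (assumed) | Rejection rate |
|---|---|
| None (same as one common window) | 4.3–4.7% |
| 10% vs 10% | 4.4–4.9% |
| 10% vs 30% | 6.5–13.9% |
| 10% vs 50% | 13.6–40.5% |

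The simulation imposes the imbalance and makes closure independent of an infant's own drainage. It shows that imbalance matters. It does not show that imbalance will occur.

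**The case against.** The strongest reply is that the definition is consistent once its limits are read together. That stands for chests closed in the OR and chests never closed. A reader might infer that a closed chest starts its clock in the OR at closure, so that an assumed 0.5 to 1 hour before exit at 10 cc/kg/hr adds 5 to 10 cc/kg. The documents do not support this. That drainage is neither in the ICU nor postoperative as the Endpoints section uses the term. In addition, 10 cc/kg/hr is the threshold for significant bleeding, not an expected rate.

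The second reply is that the open-chest rule may mean not closed when surgery ends. An infant closed later in the CICU would then keep the full 24 hours. Footnote 3, which places closure time among intraoperative data, fits that reading. It is reasonable, and may be what was meant, but the text does not say it.

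A reader might also infer that footnotes 5 and 6 define the endpoint as OR plus CICU loss. They do not: one gives assessment frequency and the significant-bleeding rate, the other asks for a 24-hour total with no start. What remains is a mismatch of labels between EBL and chest tube drainage.

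Finally, bias is not established. That bleeding influences closure is a plausible inference, but the documents do not state it, and they give no closure data by arm or overall.

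**Conclusion.** The concern holds for one group: infants whose sternum is open at OR exit and closed in the CICU within 24 hours. For them the literal rule discards all drainage before closure, for example 12 of 24 hours for an assumed closure at hour 12. The label EBL also leaves it unclear whether OR loss counts.

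The effect on the trial is added noise, and bias only if closure frequency or timing differs between arms. Its size is unknown: every closure time, drainage profile and frequency used above is an assumption. It would be going too far to conclude that the primary comparison is biased, or that the start time conflicts for all infants. Severity: should-fix.

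**What to change.** In the Endpoints, Drug protocol and Patient Assessment sections and in Schedule of Events footnote 6, give one definition for every infant regardless of sternal status: chest tube drainage in cc/kg from OR exit to 24 hours after OR exit. Delete the closure condition and the separate open-chest rule.

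State that OR blood loss is not part of this endpoint. Loss from study drug to OR exit can be reported separately, since the hypothesis refers to peri-operative bleeding. Report sternal status at OR exit by arm, descriptively.

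The cost is wording only. CICU drainage is already recorded hourly, OR loss every 15 minutes, and footnote 3 already lists time in and out and sternal closure time. No CICU closure time is needed, and clinical care does not change. Early OR loss stays outside the primary endpoint, which is why it should be reported alongside.

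### Item 2 of the primary safety endpoint cannot count an infant who dies or leaves hospital without ever being extubated, unless a cardiac arrest is recorded, and death is not a component.

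*Combined protocol and SAP*

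**What the plan says.** The Endpoints section lists the safety events by category: "any clinical signs of central or peripheral thromboembolism, respiratory or circulatory failure, or allergic reactions during hospital stay", plus blood-borne infection. It gives no working definition of either failure.

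Patient Assessment supplies one. It opens with "The primary safety endpoint is a clinical adverse event. Clinical adverse events are defined as" and then gives four items: thromboembolism, respiratory or circulatory failure, allergic reaction, and blood-borne infection. Item 2 mentions continuous monitoring of breathing and circulation in the ICU, but no value of any monitored parameter produces an event. The two operative sentences are "Respiratory failure will be defined as the need for reintubation after extubation. Circulatory failure will be defined as cardiac arrest".

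Death is not listed in either section. Adverse events are followed to discharge, and a phone call about 60 days later asks about further events. Ventilation is captured separately, as the secondary endpoint "the number of post-op hours requiring ventilator support", and the Schedule of Events has a row for its duration. Note 14 to that schedule asks for all untoward events to be reported from consent onward.

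**The concern.** Reintubation requires an earlier extubation. Only infants who reach extubation can have the respiratory event, and reaching it is an outcome that follows randomisation. An infant who never reaches it, which is among the worst respiratory courses, is scored like one who recovered without incident. With no death component, a death before extubation enters item 2 only if a cardiac arrest is recorded, and the plan does not say whether the terminal event of a death counts as one.

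At stake is the reading of the primary safety comparison. If treatment changes how many infants are extubated, the reintubation count changes for that reason alone. It could make a harmful treatment look neutral, or make a treatment that helps more infants reach extubation look worse.

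**Working it through.** **Inputs.** Item 2 and the four-item list come from Patient Assessment. The planned 15 per group is from Randomization. Fisher's exact test for categorical variables and the 0.05 threshold are from Statistical Analyses. The plan states no event rate, power or target difference for the safety endpoint, so it has no figure to reproduce.

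**Step 1: apply the rule to each course up to death or discharge.**

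| Course | Respiratory part | Circulatory part |
|---|---|---|
| Extubated, not reintubated, no arrest | no event | no event |
| Extubated, reintubated once, no arrest | event | no event |
| Ventilated for long, then extubated in hospital | still able to have the event | event only if arrest |
| Never extubated, arrest recorded | cannot occur | event |
| Never extubated, no arrest recorded | cannot occur | no event |

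The last row is the gap. It is confined to infants who die or are discharged without extubation. Circulatory failure short of arrest also goes uncounted, in every row.

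**Step 2: direction of the distortion.** Let u be the proportion of an arm never extubated by death or discharge, and r the reintubation risk among those extubated.

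- Reported proportion with respiratory failure = (1 − u) × r. It falls as u rises.
- Proportion never extubated or reintubated = u + (1 − u) × r. It rises as u rises.

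Hold r fixed and move one infant of 15 from extubated to never extubated. Then u rises by 1/15 = 6.7 points. The reported proportion falls by 6.7 × r points, while the combined proportion rises by 6.7 × (1 − r) points. The two measures never move the same way. If treatment lowers u, the signs reverse, so neither arm is favoured by design.

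**Step 3: what one infant can do to the test.** This assumes exactly 15 per arm and a two-sided test (the plan does not state sidedness). The counts are illustrative.

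| Events | Fisher p |
|---|---|
| 5 v 0 | 0.042 |
| 4 v 0 | 0.100 |
| 7 v 1 | 0.035 |
| 6 v 1 | 0.080 |

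In each pair, leaving one infant uncounted moves the result across 0.05. This shows sensitivity, not likelihood. With fewer events it changes nothing in significance terms: 4 v 1 gives p = 0.33, already far from the threshold.

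**The case against.** Most of the case on the other side is right, and it limits the point.

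- **A reader might infer that a never-extubated infant has no primary safety event at all.** The documents do not support that. Thromboembolism, allergic reaction and blood-borne infection still count, and so does a cardiac arrest. Many deaths may enter by the last route.
- **A reader might infer that item 2 would hide pulmonary embolism or myocardial infarction**, which Potential Risk names among the most severe reactions. That section classes both as thrombotic, so if recognised they fall under item 1 whether or not the infant is extubated.
- **A reader might see a contradiction between Endpoints and Patient Assessment.** The reference to clinical signs in Endpoints can attach to thromboembolism alone, and item 1 uses it that way. The two sections read as a general statement followed by its definition.
- **A reader might infer a bias towards safety.** Step 2 shows that the distortion can go either way.
- **A reader might think the stopping rule is weakened.** Stopping Criteria uses thromboembolic events only.
- **The data are not lost.** Ventilator hours and untoward events are recorded, and safety data are reviewed after 10, 20 and 30 subjects. This stands, but these records lie outside the primary safety count. Ventilator hours are an imperfect substitute, because the plan gives no rule for infants who die while ventilated and an early death yields a short duration.
- **Hard, observable events are a defensible choice**, since the Safety Team is unblinded after 24 hours. This also stands. Death is such an event, so adding it keeps that advantage.

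Nothing in this list supplies a score for the infant in the last row of the Step 1 table.

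**Conclusion.** The point holds, within limits. Followed exactly, item 2 scores as event-free an infant who dies or leaves hospital without extubation and with no recorded arrest, and no other component counts the death itself. Because extubation follows randomisation and may depend on treatment, the comparison of this component between arms can be distorted.

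The size cannot be estimated. The documents give no rate for death, failure to extubate or reintubation, and they do not say when infants are normally extubated. What can be said is that each infant is 6.7 points in an arm of 15, and that one infant can cross the significance threshold at some counts. Those statements assume the planned 15 per arm and, for the p-values, a two-sided test. This is a gap in the scoring of the endpoint that should be closed.

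**What to change.** In Patient Assessment, count death from any cause during the hospital stay as a primary safety event; at minimum, count death before extubation. Beside the reintubation count, report for each arm the number of infants never extubated by death or discharge. Carry the same wording into Endpoints.

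Whether prolonged ventilation, or circulatory failure without arrest, should also count, and by what criteria, is a clinical choice. The sponsor's clinical team should settle it in writing before unblinding, and in any case before anyone sees event counts by group.

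The cost is protocol wording and, if needed, a case report form field for death and for extubation status at discharge. Ventilation duration is already collected and no procedure is added. The small downside is a possibly higher event count in either arm.
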